## 4.4 Dose and Schedule Rationale

Administration of TLR7 agonists results in the activation of pDCs followed by their transient depletion. Consequently, the pool of excitable pDCs has to be replenished by expanding and maturing precursor cells from the bone marrow (Markov et al, 2016), a process which takes about 7 days (Bourquin et al, 2011; Tsitoura et al, 2015). It has been described for other TLR7 agonists that this may result in tachyphylaxis, meaning that within this time period, additional administrations will not result in further secretion of IFN $\alpha$  (Bourquin et al, 2011; Tsitoura et al, 2015). To avoid this mechanism and yet ensure frequent stimulation of the immune system, BNT411 will be administered once weekly in the first 4 cycles. These 4 cycles are considered to induce a sufficient immune response. Consequently, BNT411 is applied every 3 weeks as a maintenance therapy after the first 4 cycles instead of every week.

BNT411 will be administered as a 30-minute infusion in the clinic. Preclinical experiments revealed acute adverse effects at lower doses when administered as bolus injection but not as infusion, while pharmacodynamic parameters remained comparable, irrespectively of the duration of compound administration.

The BNT411 starting dose of  $0.05 \mu g/kg$  is calculated based on a minimally anticipated biologic effect level (MABEL) approach with an additional safety factor of 25:

- Upon BNT411 exposure, IFNα-secretion is the earliest detectable pharmacodynamics marker in human whole blood preparations.
- 4 nM is the minimal effective concentration (MEC) of BNT411 needed to induce IFN $\alpha$  in this *in vitro* setting (Studies R-19-0027 and R-19-0028), which equals approximately a human plasma  $C_{max}$  of 2 ng/mL.
- To reach this target plasma concentration, an intravenously applied dose of 1.25 μg/kg is required (based on human pharmacokinetic modeling with animal data; Study BNSM2018002). This dose equals approximately dose level 4 (1.2 μg/kg).
- A safety factor of 25 is applied, resulting in the proposed human starting dose of 0.05 μg/kg.

Based on the nonclinical toxicological profile, which does not indicate a steep dose- or exposure-response curve and does not show any severe toxicity findings, an initial dose tripling for the accelerated titration design in the dose escalation phase Part 1A is suggested. Following this, standard dose doubling is suggested starting from dose level 4 in line with the FDA Guidance for Industry S9 Nonclinical Evaluation for Anticancer Pharmaceuticals. Based on nonclinical data and as described in the MABEL approach, dose level 4 (1.2  $\mu$ g/kg) is the anticipated minimal efficacious dose.

Information relating to COVID-19 vaccinations including a risk-benefit assessment and guidance for vaccination during this clinical trial is provided in Sections 10.8 and 10.9.

More details on the dose and schedule rationale can be found in the Investigator's Brochure.

#### 4.5 End of Trial Definition

The trial will be considered completed once all patients have completed treatment and safety follow-ups. After the sponsor considers the data collection is completed, patients will continue to follow the SoA defined by the protocol unless the medical monitor gives approval not to do so.

# 5 Trial Population

## 5.1 Inclusion Criteria

Each patient who meets all of the following criteria is eligible to enroll in the trial.

#### For Part 1A:

1. Histologically confirmed solid tumor (cytology is allowed for NSCLC, SCLC and pancreatic cancer) that is metastatic or unresectable and for which there is no available standard therapy likely to confer clinical benefit, or patients who are not candidates for such available therapy.

#### For Part 1B:

- 2. Histologically or cytologically confirmed ES-SCLC (per the Veterans Administration Lung Study Group [VALG] staging system) who received no prior chemotherapy for extensive stage disease.
- 3. Those treated with prior chemo/radiotherapy with curative intent for LS-SCLC should be treatment-free for at least 6 months since last chemo/radiotherapy.
- 4. No interstitial lung disease or active, non-infectious pneumonitis.

## For Both Part 1A and Part 1B

- 5. Male and female  $\geq$ 18 years of age.
- 6. Must sign an informed consent form (ICF) indicating that he or she understands the purpose of and procedures required for the trial and are willing to participate in the trial prior to any trial related assessments or procedures.
- 7. ECOG performance status of 0 to 1.
- 8. Measurable disease according to RECIST 1.1.
- 9. Albumin level at screening  $\geq 30$  g/L.
- 10. Adequate coagulation function at Screening as determined by:
  - a. International normalized ratio (INR) or prothrombin time  $\leq$ 1.5 x upper limit normal (ULN; unless on therapeutic anticoagulants with values within therapeutic window),
  - b. Activated partial thromboplastin time (aPTT)  $\leq$  1.5 x ULN (unless on therapeutic anticoagulants with values within therapeutic window).
- 11. Adequate hematologic function at Screening as determined by:
  - a. White blood count (WBC)  $\geq 3 \times 10^9/L$ ,
  - b. Absolute neutrophil count (ANC) ≥1.5 x 10^9/L (patient may not use granulocyte-colony stimulating factor (G-CSF) or granulocyte-macrophage colony stimulating factor (GM-CSF) to achieve these WBC and ANC levels),

- c. Platelet count  $\geq 100 \times 10^9/L$ ,
- d. Hemoglobin (Hgb) ≥9.0 g/dL.
- 12. Adequate hepatic function at Screening as determined by:
  - a. Total bilirubin  $\leq 1.5$  mg/dL (or  $\leq 2.0$  mg/dL for patients with known Gilbert's syndrome),
  - b. Aspartate aminotransferase (AST) and alanine aminotransferase (ALT)  $\leq$ 2.5 x ULN; or  $\leq$ 5 x ULN in patients with metastatic liver disease.
- 13. Adequate renal function at Screening as determined by:
  - a. Glomerular filtration rate (GFR) ≥60 mL/min/1.73 m²– e.g. according to the abbreviated Modification of Diet in Renal Disease (MDRD) equation:

GFR = 
$$186 \times (SCr^{-1.154}) \times (age^{-0.203})$$

(where SCr, the serum creatinine level, is expressed in mg/dL; multiplied by 0.742 if the patient is female; multiplied by 1.212, if the patient is African-American (Levey et al, 1999).

- 14. Able to attend trial visits as required by the protocol.
- 15. Women of childbearing potential (WOCBP) must have a negative serum (beta-human chorionic gonadotropin [beta-hCG]) test/value at Screening. Patients who are postmenopausal or permanently sterilized as defined in Section 10.4 can be considered as not having reproductive potential. Further guidance on contraceptive measures for female patients can be found in Section 10.4.
- 16. WOCBP must agree not to donate eggs (ova, oocytes) for the purposes of assisted reproduction during the entire trial, until 6 months after last BNT411 treatment.
- 17. A man who is sexually active with a woman of childbearing potential and has not had a vasectomy must agree to use a barrier method of birth control, e.g. either condom with spermicidal foam/gel/film/cream/suppository or partner with occlusive cap (diaphragm or cervical/vault caps) with spermicidal foam/gel/film/cream/suppository, and all men must also not donate sperm during the trial and for 6 months after receiving the last dose of BNT411 (refer Section 10.4 for further recommendations).
- 18. All patients must provide an FFPE (Formalin Fixed Paraffin Embedded) from the latest available archival tumor tissue. If such tissue cannot be provided, the sponsor's approval of enrollment is needed.

## **5.2** Exclusion Criteria

A patient who meets any of the following criteria will be excluded from trial participation.

#### **Prior and Concomitant Therapy**

- 1. Has received prior systemic therapy with a TLR7 agonist.
- 2. Has been receiving: radiotherapy, chemotherapy, or molecularly-targeted agents or tyrosine kinase inhibitors within 2 weeks or 5 half-lives (whichever is longer) of the start of trial treatment; immunotherapy/monoclonal antibodies within 3 weeks of the start of trial

treatment; any live vaccine within 4 weeks of the start of trial treatment; nitrosoureas, antibody-drug conjugates, or radioactive isotopes within 6 weeks of the start of trial treatment.

- 3. Receives concurrent systemic (oral or intravenous) steroid therapy >10 mg prednisone daily or its equivalent for an underlying condition.
- 4. Receives concurrent strong inhibitors or inducers of the cytochrome P450 enzymes.
- 5. Has had major surgery within the 4 weeks before the first dose of BNT411.
- 6. Has ongoing or active infection requiring intravenous treatment with anti-infective therapy that has been administered less than two weeks prior to first dose of trial treatment.
- 7. Has side effects of any prior therapy or procedures for any medical condition not recovered to NCI CTCAE v.5 Grade ≤1.

Notes: peripheral neuropathy Grade  $\leq 2$  is allowed; alopecia of any grade is allowed.

#### **Medical Conditions**

- 8. Current evidence of new or growing brain or leptomeningeal metastases during screening. Patients with known brain or leptomeningeal metastases may be eligible if they:
  - a. had radiotherapy, surgery or stereotactic surgery for the brain or leptomeningeal metastases,
  - b. have no neurological symptoms (excluding Grade ≤2 neuropathy),
  - c. have stable brain or leptomeningeal disease on the CT or MRI scan within 4 weeks before signing the informed consent,
  - d. are not undergoing acute corticosteroid therapy or steroid taper.

Notes: Subjects with central nervous system symptoms should undergo a CT scan or Magnetic Resonance Imaging (MRI) of the brain to exclude new or progressive brain metastases. Spinal bone metastases are allowed, unless imminent fracture with cord compression is anticipated.

- 9. Has history of seizures other than isolated febrile seizure in childhood; has a history of a cerebrovascular accident or transient ischemic attack less than 6 months ago.
- 10. Has effusions (pleural, pericardial, or ascites) requiring drainage.
- 11. Has eye pathology likely to confound observation of potential ocular AEs (refer to Ophthalmologic Manual).
- 12. Has a fever ≥38°C within 3 days before signing the ICF.
- 13. Has a history of autoimmune disease active or past including but not limited to inflammatory bowel disease, systemic lupus erythematosus (SLE), ankylosing spondylitis, scleroderma, or multiple sclerosis. Has any active immunologic disorder requiring immunosuppression with steroids or other immunosuppressive agents (e.g. azathioprine, cyclosporine A) with the exception of patients with isolated vitiligo, resolved childhood asthma or atopic dermatitis, controlled hypoadrenalism or hypopituitarism, and euthyroid patients with a history of Grave's disease. Patients with controlled hyperthyroidism must be

- negative for thyroglobulin, thyroid peroxidase antibodies, and thyroid-stimulating immunoglobulin prior to trial drug administration.
- 14. Known history of seropositivity for human immunodeficiency virus (HIV) with CD4+ T-cell (CD4+) counts <350 cells/uL and with a history of acquired immunodeficiency syndrome (AIDS)-defining opportunistic infections.
- 15. Known history/positive serology for hepatitis B requiring active anti-viral therapy (unless immune due to vaccination or resolved natural infection or unless passive immunization due to immunoglobulin therapy). Patients with positive serology must have Hepatitis B virus (HBV) viral load below the limit of quantification.
- 16. Active Hepatitis C virus (HCV) infection; patients who have completed curative antiviral treatment with HCV viral load below the limit of quantification are allowed.
  - Notes: Country specific criteria for Germany To confirm that a patient would be eligible, an active infection with HIV/Hepatitis B or C should be ruled out by serum blood test at screening (see Section 12.2.1).
- 17. Has a known hypersensitivity to a component of BNT411 drug product, or another similar compound.
- 18. Has another primary malignancy that has not been in remission for at least 2 years, with the exception of those with a negligible risk of metastasis or death (such as adequately treated carcinoma in situ of the cervix, basal or squamous cell skin cancer, localized prostate cancer, or ductal carcinoma in situ).

Note: should be discussed with Medical Monitor in case of uncertainties.

#### **Other Comorbidities**

- 19. Has abnormal electrocardiograms (ECGs) that are clinically significant, such as Framingham-corrected QT interval >480 ms.
- 20. In the opinion of the treating investigator, has any concurrent conditions that could pose an undue medical hazard or interfere with the interpretation of the trial results; these conditions include, but are not limited to:
  - a. ongoing or active infection requiring antibiotic/antiviral/antifungal therapy,
  - b. concurrent congestive heart failure (New York Heart Association [NYHA] Functional Classification Class III or IV),
  - c. concurrent unstable angina,
  - d. concurrent cardiac arrhythmia requiring treatment (excluding asymptomatic atrial fibrillation).
  - e. acute coronary syndrome within the previous 6 months,
  - f. significant pulmonary disease (shortness of breath at rest or on mild exertion) for example due to concurrent severe obstructive pulmonary disease.
- 21. Has a cognitive, psychological or psychosocial impediment that would impair the ability of the patient to receive therapy according to the protocol or adversely affect the ability of the

patient to comply with the informed consent process, protocol, or protocol-required visits and procedures.

22. Is pregnant or breastfeeding.

# Exclusion criteria added with amended protocol version 3.0 (Prior and Concomitant Therapy)

23. Has any contraindication to atezolizumab, carboplatin or etoposide as per USPI or SmPC in Part 1B.

# 5.3 Screen Failures

Screen failures are defined as patients who consent to participate in the clinical trial but are not subsequently entered in the trial. A minimal set of screen failure information is required to ensure transparent reporting of screen failure patients to meet the Consolidated Standards of Reporting Trials (CONSORT) publishing requirements and to respond to queries from regulatory authorities. Minimal information includes demography, the reason(s) for screen failures, eligibility criteria, and any serious adverse event (SAE).

Patients who fail their first screening for trial eligibility may qualify for two re-screening opportunities (a total of three screenings per patient) at the investigator's discretion. Patients must re-sign the informed consent form prior to re-screening. Results of standard-of-care tests or examinations performed prior to obtaining informed consent and within 28 days prior to the treatment may be used; such tests do not need to be repeated for screening or re-screening.

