- 11 On-treatment imaging will be performed at Week 6 (+7 days), every 6 weeks (±7 days) for 48 weeks, and every 12 weeks (±7 days) thereafter until disease progression is assessed by the investigator (unless the investigator elects to continue treatment [see Section 8.5.1 for conditions of continued treatment]), withdrawal of consent, trial termination by the sponsor, or death, whichever occurs first, regardless of whether patients start a new anti-cancer therapy. Refer to Sections 10.5 and 10.6 of the protocol for RECIST 1.1. and iRECIST imaging and treatment guidelines.
- 12 ECOG status should be assessed before drug administration.
- 13 Adverse events (AEs) and serious adverse events (SAEs) should be reported from the time of signing the informed consent to 60 days (±7 days) after the patient receives the last dose of BNT411.
- 14 Suspected BNT411-related AEs only. Furthermore, in Germany only, all SAEs that occur in the patient throughout his or her lifetime should be reported refer to Table 1-5 and Section 10.3.4 for further details.
- 15 Patients who experience a delay in the administration of BNT411 should return to the clinic at least every 2 weeks (±3 days) and assessments listed under 'unscheduled visit' should be performed and reported in the eCRF. Unscheduled visit assessments should be performed at the investigator's discretion. For information on COVID-19 vaccination during the trial, see Section 10.9.
- 16 All labs at the screening visit must be obtained within 7 days of Cycle 1 Day 1. All lab assessments except for PK and biomarkers are done locally.
- 17 Laboratory samples should be obtained up to 3 days before treatment administration.
- 18 TSH, free-T3 and free-T4 will only be measured at screening, Cycle 1 Day 1, Cycle 2 Day 1, and on Day 1 of every evenly numbered cycle thereafter.
- 19 Serum pregnancy test is performed at screening. Thereafter, urine pregnancy test is sufficient unless indicated otherwise. The frequency of testing during treatment phase may depend on clinical indication per investigator's assessment and may also depend on local guidelines and regulations.

- 20 Medical history includes cancer history.
- 21 Prior/Concomitant Medications and Non-Drug Therapies include all anti-cancer pre-treatments.
- 22 Prior/Concomitant Medication and Non-Drug therapies only for BNT411 related AEs.

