#### **8 Trial Assessments and Procedures**

- Trial procedures and their timing are summarized in the SoA. Protocol waivers or exemptions are not allowed.
- Immediate safety concerns should be discussed with the sponsor immediately upon occurrence or awareness to determine if the patient should continue or discontinue trial treatment.
- Adherence to the trial design requirements, including those specified in the SoA, is essential and required for trial conduct.
- All screening evaluations must be completed and reviewed to confirm that potential
  patients meet all eligibility criteria. The investigator will maintain a screening log to
  record details of all patients screened and to confirm eligibility or record reasons for
  screening failure, as applicable.
- Procedures conducted as part of the patient's routine clinical management (e.g. blood count) and obtained before signing of the ICF may be utilized for screening or baseline purposes provided the procedures met the protocol-specified criteria and were performed within the time frame defined in the SoA.
- In case the COVID-19 pandemic creates challenges that may interfere with the conduct of this clinical trial, the addendum "Clinical trial protocol addendum related to COVID-19 pandemic Version 3.0 04 Jun 2021" gives guidance and outlines assistance on protocol procedures, patient enrollment and requirements within the established protocol.
- Information relating to COVID-19 vaccinations including a risk-benefit assessment and guidance for vaccination during this clinical trial is provided in Sections 10.8 and 10.9.

The schedule of assessments to be performed in Parts 1A and 1B of the trial are summarized in Table 1-1 to Table 1-8 in Section 1.3.1. With the exception of post-dose blood and urine sampling for PK assessments, all assessments should be performed before trial treatment administration (on the applicable days) or any planned intervention. On the days of tumor imaging, blood sampling can be before or after imaging assessments.

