# 8.1 Screening Procedures

Informed consent must be obtained within 21 days before Day 1 of Cycle 1 of Part 1 (A or B). Patients must provide written informed consent before any other screening-specific assessments are performed. Trial sites must maintain a log of all consenting patients which will include date and time of consent.

Consenting patients who meet eligibility criteria will be enrolled in the trial and will be assigned a patient number.

Screening assessments will be performed as summarized in Table 1-1 and Table 1-2. Screening will be initiated and completed within 21 days before Day 1 of Cycle 1 for Parts A and B.

Women of child-bearing potential must have a negative serum pregnancy test conducted at screening.

Vital signs and ECG will be performed as described in Sections 8.6.2 and 8.6.3.

Laboratory safety tests (hematology, biochemistry, coagulation, endocrine [thyroid stimulating hormone (TSH), triiodothyronine (T3) and thyroxine (T4) and urinalysis) will be assessed as described in Section 8.6.4.

All patients will have a CT-scan with contrast or MRI of thorax, abdomen, and pelvis during screening. Evaluation of left ventricular function, either by echocardiogram (ECHO) or multigated acquisition (MUGA) scan, will be performed at Screening (or within 21 days of screening) and as clinically indicated at other time points. Head and neck imaging is also required for patients with squamous cell carcinoma of the head and neck (SCCHN). Imaging of the pelvis is not required for patients with SCCHN but is strongly recommended. If a CT scan or MRI has been performed within 21 days before visit Cycle 1 Day 1 as part of standard procedure, it is acceptable as a screening scan for the trial. If there is suggestion of brain metastases/tumors, a CT-scan or MRI of the head and neck will be performed within 21 days before the Cycle 1 Day 1 visit. Scans that exceed the 21-day window may be used for trial enrollment with sponsor approval.

Note: country specific information for Germany.

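### Protocol Section 5.3 lets tests up to 28 days old serve for screening without repeat, contradicting the 7-day laboratory window in the SoA and Sections 8 and 8.1

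*Protocol*

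**What the plan says.** Four places in the protocol govern how old a screening test may be.

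- **Section 5.3 (Screen Failures).** Standard-of-care results obtained before consent and "within 28 days prior to the treatment may be used; such tests do not need to be repeated for screening or re-screening". Laboratory tests are not carved out.
- **SoA, Section 1.3.1.** Footnote 16 to Table 1-1 (Part 1A) and footnote 19 to Table 1-2 (Part 1B) both state: "All labs at the screening visit must be obtained within 7 days of Cycle 1 Day 1".
- **Section 8.1.** "Screening will be initiated and completed within 21 days before Day 1 of Cycle 1 for Parts A and B".
- **Section 8.** Routine tests done before consent, with a blood count as the example, may serve for screening or baseline "provided the procedures met the protocol-specified criteria and were performed within the time frame defined in the SoA".

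The protocol states one exception to the 21-day limit: imaging scans, with sponsor approval. ECHO/MUGA has its own timing, counted back from Screening and not from Cycle 1 Day 1.

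Two other provisions bear on the consequence. Inclusion criteria 9 to 13 (albumin, coagulation, hematologic, hepatic and renal function) are judged at Screening. Exclusion 2 bars "radiotherapy, chemotherapy, or molecularly-targeted agents or tyrosine kinase inhibitors within 2 weeks or 5 half-lives (whichever is longer) of the start of trial treatment".

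**The concern.** Sections 5.3 and 8 address the same tests, those done in routine care before consent, and give different answers. Section 5.3 is the more permissive, and it is the only one of the four that speaks directly to re-screening. A site handling a re-screened patient may well turn to it first.

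The organ-function criteria are meant to describe the patient close to the first dose of a first-in-human agent. If a site applies the 28-day allowance to labs, those criteria can be met on values that predate the patient's last prior treatment.

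The conflict also blurs deviation reporting. SAP Section 7.2 defines a protocol deviation as a failure to meet the eligibility criteria or protocol requirements. A screening lab from Day −20 complies with Section 5.3 and breaches the SoA, so its classification depends on which text is read.

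**Working it through.** The plan gives no figure of its own on this point, so the check compares the windows with the washouts.

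**Inputs**
- Look-back: 28 days (Section 5.3), 21 days (Section 8.1), 7 days (SoA footnotes 16 and 19).
- Washout from exclusion 2: 2 weeks or 5 half-lives, whichever is longer, for chemotherapy, radiotherapy and targeted agents; 3 weeks for immunotherapy and monoclonal antibodies; 6 weeks for nitrosoureas, antibody-drug conjugates and radioactive isotopes.
- The documents give no half-lives for prior agents, so the washout is treated as an assumption and varied.

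**Size of the conflict.** 28 / 7 = 4 times the SoA laboratory window. 28 − 21 = 7 days beyond the overall screening window.

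**Can a qualifying test predate the last permitted dose?** Greatest lead = look-back − washout. A positive value means that the test can come first.

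| Washout | Look-back 28 d | Look-back 21 d | Look-back 7 d |
|---|---|---|---|
| 14 d (half-life up to 14/5 = 2.8 d) | 28 − 14 = 14 d | 21 − 14 = 7 d | 7 − 14 = −7: never |
| 21 d (half-life 21/5 = 4.2 d, or the 3-week classes) | 28 − 21 = 7 d | 21 − 21 = 0: never | 7 − 21 = −14: never |
| 28 d (half-life 28/5 = 5.6 d) | 28 − 28 = 0: never | 21 − 28 = −7: never | 7 − 28 = −21: never |
| 42 d (the 6-week classes) | 28 − 42 = −14: never | 21 − 42 = −21: never | 7 − 42 = −35: never |

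The 14-day lead is the extreme, with the last dose on Day −14. A last dose on Day −15 and a count on Day −28 give 28 − 15 = 13 days.

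**Which part of the trial.** Part 1B admits no prior chemotherapy for extensive-stage disease, and requires at least 6 months off treatment after curative-intent therapy for limited-stage disease (inclusion 2 and 3). The chemotherapy scenario is therefore confined in practice to Part 1A. The conflict in the text applies to both parts.

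**With labs held to the SoA window.** The oldest usable value is from Day −7 and the last permitted dose is at Day −14 or earlier, so every qualifying value is at least 14 − 7 = 7 days after that dose. The lead disappears.

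**The case against.** The strongest reply is that the stricter rules govern anyway. Section 8 deals with exactly these tests and ties them to the SoA, the SoA wording is mandatory, and Section 8 also disallows waivers and calls adherence to the SoA essential. This stands to the extent that the consequence arises only where a site follows Section 5.3 over the other three. It does not remove the conflict: no passage sets an order of precedence, and Section 5.3 says that no repeat is needed.

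The second reply is that other safeguards catch the patient. Exclusion 7 bars anyone whose side effects from prior therapy have not recovered to Grade 1 or lower (with stated exceptions), and it is not tied to Screening. Hematology, biochemistry and coagulation are scheduled at Cycle 1 Day 1, drawn up to 3 days before dosing, and Section 6.1.1 requires assessments to be complete before the infusion. These are real mitigations, but partial. Exclusion 7 works in CTCAE grades and covers only effects of prior therapy, while inclusion 9 to 13 set specific laboratory limits at Screening. No passage says that those limits are re-applied to the Cycle 1 Day 1 values.

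A reader might infer more: that a cytopenia carried over from earlier chemotherapy would be counted as a DLT, alter a 3+3 decision, or end the single-patient cohorts. The documents do not support that. Section 10.3.3 records clinically significant conditions present at baseline as medical history. Baseline is the last value before the first dose (Section 9.4.1; SAP Section 8.1), normally the Cycle 1 Day 1 draw. An event already present is treatment-emergent only if it worsens (Section 9.4.2; SAP Section 8.5.2). Worsening after dosing is equally possible under the 7-day rule, for example with chemotherapy on Day −15 and a count on Day −7. That risk is not created by the 28-day allowance.

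**Conclusion.** The point holds as an inconsistency in operative protocol text that should be corrected. Section 5.3 allows a test age that the SoA, Section 8 and Section 8.1 do not: 28 days against 7 for labs and 21 for screening overall.

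Its practical reach is limited. If a site applies Section 5.3 to labs, a Part 1A patient with a 14-day washout could meet inclusion 9 to 13 on values from up to 14 days before the last permitted chemotherapy dose. The lead falls to 7 days at a 21-day washout and to nothing at 28 days or more. This rests on two assumptions: that the site gives Section 5.3 priority, and that five half-lives of the prior agent do not exceed 14 days.

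The documents do not show that patients qualify this way as a matter of course, or that dose escalation is affected.

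**What to change.** In Section 5.3, replace the 28-day limit with a cross-reference to the time frame that the SoA sets for the assessment concerned, and state that a test outside its window is repeated at screening or re-screening. This brings Section 5.3 into line with Sections 8 and 8.1 and introduces no new window.

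Use a cross-reference, not a flat 21-day figure for everything other than labs. A flat figure would collide with the ECHO/MUGA timing and with the provision for older scans with sponsor approval, both of which should stay. No separate rule on tests taken before the last anticancer dose is needed for labs, because the 7-day window already ensures that they follow that dose.

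The cost is one sentence in an amendment and a few repeat local blood tests that the SoA already requires. If enrolment has closed, the useful step is to identify patients who qualified on labs older than 7 days and classify them consistently under SAP Section 7.2.
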